Table 1.Registry Activities

Activity	Registry Enrollment	Month ^a	Month ^a	Month ^a	Month ^a 18, 24, 30, 36, 42, 48, 54	Month ^a	Month ^a 66, 72, 78, 84, 90, 96, 102, 108, 114	Upon Completion Month ^a 120 or Premature Discontinuation	At Time of Reported Event
Inclusion/Exclusion Criteria	X								
Informed Consent	X								
Demographics	X								
Medical History and Treatment Modality	X								
Safety Data Collection (AEs of Special Interest/SAEs)	X	X	X	X	X	X	X	X	X
Prior and Concomitant Psoriasis Medications	X	X	X	X	X	X	X	X	X
Concomitant Medications at Time of Reported SAE or AE of Interest	X	X	X	X	X	X	X	X	X
Physician Global Assessment	X	X	X	X	X	X	X	X	
PROs ^b									
Patient Global Assessment	X	X	X	X	X	X	X	X	
DLQI	X		X	X	X ^c	X	X ^c	X	
PHQ-9	X		X	X	X ^c	X	X ^c	X	
Healthcare Resource Utilization (Unscheduled Outpatient Visits, Emergency Room Visits and Hospitalizations Questionnaire)	X		X	X	X ^c	X	X ^c	X	
WPAI	X		X	X	X ^c	X	X ^c	X	

[figure not shown]

Table 1. Registry Activities (Continued)

Activity	Registry Enrollment	Month ^a	Month ^a	Month ^a	Month ^a 18, 24, 30, 36, 42, 48, 54	Month ^a	Month ^a 66, 72, 78, 84, 90, 96, 102, 108, 114	Upon Completion Month ^a 120 or Premature Discontinuation	At Time of Reported Event
Rosenberg Self-Esteem Scale	X			X		X		X	
Census Socio-Demographic Questionnaire	X					X		X	
Medical Outcomes (MOS)-Social Activities Scale	X			X		X		X	
Psoriasis Impact and Experience	X			X		X		X	
Illness Cognition Questionnaire	X			X		X		X	
Insurance Status	X			X		X		X	
Case Report Form Completion	X	X	X	X	X	X	X	X	X

a. Data collection at regular visits that are closest to time points described. For patients participating in the direct to HCP process, follow-up is annually and AEs of Special Interest and AEs of Special Interest that lead to permanent discontinuation of HUMIRA®, surgeries, hospitalizations, deaths and medications taken for psoriasis will be collected.

b. Only sites in the US will conduct PRO assessments.

c. Data collected at annual visits only (i.e., Months 24, 36, 48, 60, 72, 84, 96, and 108).

The procedures outlined in Table 1 are discussed in detail in this section, with the exception of the collection of AE information, which is discussed in Section 7.0 and Patient Informed Consent, which is discussed in Section 8.0.

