7.1.2 Adverse Events of Special Interest

Table 2. AEs of Special Interest for This Registry

Serious and non-serious opportunistic infections, including the following bacterial, fungal, viral and parasitic infections: Aspergillus, Blastomyces, Candida, Coccidioides, Cryptococcal, Cytomegalovirus, Histoplasma, Listeria, Nocardia, Paracoccidioides, Pneumocystis, Toxoplasma, Tuberculosis, Herpes, Bacillary angiomatosis, Mucormycosis, Progressive Vaccinia, Zygomycosis, BK virus, and JC virus

L	y	m	ıp	h	O.	m	ıa

Hepatosplenic T-cell lymphoma

Leukemia

Non-melanoma skin cancer (NMSC)

Other malignancies (except lymphoma, leukemia and NMSC)

Immune reactions including lupus, lupus-like reactions, and severe allergic reactions

Congestive heart failure (CHF)

Cerebrovascular accident (CVA)

Myocardial infarction (MI)

CNS demyelinating disorders (including MS and Guillain-Barré syndrome)

Hepatic events that are serious or lead to permanent discontinuation of HUMIRA (e.g., persistent liver function test abnormalities, acute liver failure and other serious hepatic events)

Hematologic events that are serious or lead to permanent discontinuation of HUMIRA (e.g., aplastic anemia, Granulocytopenia, Granulocyte Maturation Arrest, Leukopenia, Neutropenia, Pancytopenia and Thrombocytopenia)

Worsening of Psoriasis

Vasculitis

Diverticulitis

Intestinal perforation

In addition, to the SAEs and AEs of Special Interest (Table 2), AEs that lead to permanent discontinuation of HUMIRA® will be collected.

Psoriasis HUMIRA® Registry

For patients participating in the direct to HCP process in addition to surgeries, hospitalizations, deaths, and the events listed as AEs of Special Interest (Table 2), AEs of Special Interest that lead to permanent discontinuation of HUMIRA® will be collected.

During the course of the registry, additional AEs of Special Interest may be identified by AbbVie. Updates to the AEs of Special Interest will be maintained and collected through the eCRF system. Sites will be trained on all updates to the eCRF system.

The physician will assess and record any additional information on the AEs of Special Interest in detail on the AE of Special Interest eCRF.

The physician will assess all reported AEs for seriousness and follow the requirements/timelines for reporting any AE that fulfills the criteria of an SAE, as defined in Section 7.1.3.

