The physician will assess and record any AE of Special Interest and/or SAE in detail on the Adverse Event eCRF, including the date and time of onset, description, severity, time course, duration and outcome, relationship of the AE to drug, information specific to the event, final diagnosis/syndrome (if known), and any action(s) taken. For all AEs of Special Interest, the physician must pursue and obtain all the above-mentioned information in order to adequately determine the outcome of the AE and to assess whether it meets the criteria for classification as an SAE as well as to determine a causal relationship. Follow-up safety queries will be issued to sites three times and considered closed after the next scheduled quarterly monitor contact per approval of the medical monitor listed in Section 1.0. In the event of a death, follow-up will include an autopsy report, if available, and a death certificate.

Obvie HUMIRA® (adalimumab) P10-023 Protocol Amendment 3 Psoriasis HUMIRA® Registry

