7.2 Severity

The physician will use the following definitions to rate the severity for any AE of Special Interest being collected as an endpoint/data point in the registry and for all SAEs.

Mild The adverse event is transient and easily tolerated by the patient.

Moderate The adverse event causes the patient discomfort and interrupts

the patient's usual activities.

The adverse event causes considerable interference with the Severe

patient's usual activities and may be incapacitating or

life-threatening.

7.3 **Relationship to Pharmaceutical Product**

The physician will use the following definitions for any AE of Special Interest being collected as an endpoint/datapoint in the registry and for all SAEs, to assess the relationship of the AE to the use of HUMIRA®. For all SAEs and AEs of Special Interest with a possible or probable causal relationship to HUMIRA® treatment, follow-up by the physician is required until the event or its sequelae resolve or stabilize at a level acceptable to the physician:

Probably Related An adverse event has a strong temporal relationship to

pharmaceutical product or recurs on re-challenge and another

cause of event is unlikely or significantly less likely.

Possibly Related An adverse event has a strong temporal relationship to the

pharmaceutical product and another cause of event is equally or

less likely compared to the potential relationship to drug.

Probably Not

An adverse event has little or no temporal relationship to the Related

pharmaceutical product and/or a more likely other cause of

event exists.

Not Related An adverse event is due to an underlying or concurrent illness or

> effect of another drug and is not related to the pharmaceutical product (e.g., has no temporal relationship to drug or has a much

more likely other cause of event).

If an Investigator's opinion of possibly, probably not, or not related to pharmaceutical product is given, an Other cause of event must be provided by the Investigator for the SAE.

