10.3.4 Analysis of Observational AEs Excluding HCP Process

The analysis will be performed using data from first day in the registry through the last contact, excluding the HCP process. The number and percentage of patients experiencing SAEs, AEs of Special Interest and AEs that lead to permanent discontinuation of HUMIRA® will be tabulated by body system and Medical Dictionary for Drug Regulatory Activities (MedDRA®) preferred term. Rates (event per 100 patient-year of observation) of SAEs, AEs of Special Interest and AEs that lead to permanent discontinuation of HUMIRA® and the 95% confidence interval will be provided.

Summaries of SAEs, AEs of Special Interest and AEs that lead to permanent discontinuation of HUMIRA® by severity and relationship to HUMIRA® will be provided.

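### Section 10.3.4 promises severity and relationship summaries for AEs leading to permanent discontinuation, but Sections 7.1.3, 7.2 and 7.3 require those ratings only for SAEs and AEs of Special Interest

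*Protocol*

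**What the plan says.** The safety analyses in Section 10.3 work with three event classes: SAEs, AESIs, and AEs that lead to permanent discontinuation. The last sentence of Section 10.3.4 commits to summaries of SAEs, AESIs and "AEs that lead to permanent discontinuation of HUMIRA® by severity and relationship to HUMIRA® will be provided".

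The third class is a collected class in its own right. Section 7.1.2 states that, beyond SAEs and the Table 2 events, "AEs that lead to permanent discontinuation of HUMIRA® will be collected". Section 7.4 has these events reported to the sponsor.

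The rating instructions name only two classes. Under Section 7.2 the physician uses the definitions "to rate the severity for any AE of Special Interest being collected as an endpoint/data point in the registry and for all SAEs". Section 7.3 applies its definitions "for any AE of Special Interest being collected as an endpoint/datapoint in the registry and for all SAEs, to assess the relationship". Section 7.1.3, whose list of items includes severity and relationship to drug, says: "The physician will assess and record any AE of Special Interest and/or SAE in detail on the Adverse Event eCRF". The monitoring sentence in Section 7.0 and the Table 1 row, "Safety Data Collection (AEs of Special Interest/SAEs)", also name only those two.

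**The concern.** The analysis section and the collection sections do not cover the same events. An event that ended therapy but was neither serious nor on the AESI list must be collected and reported, yet nothing tells the site to rate its severity or its relationship to the drug. Section 10.3.4 then plans to summarise it by both.

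Whether such an event is attributed to the drug is a natural question in a registry whose primary objective is long-term safety (Section 5.0). A statistical analysis plan cannot supply ratings that sites were not asked to make, and over a follow-up of up to ten years they would be hard to reconstruct reliably. Sites that rate unprompted would fill some cells and other sites would not. With about 300 + 100 = 400 physicians expected (Section 6.3), the missing entries would partly reflect site habit.

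**Working it through.** The point depends on no sample size, power or event count, so the check is a comparison of sections.

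| Duty or output | Protocol section | SAEs | AESIs | Discontinuation AEs that are neither |
|---|---|---|---|---|
| Collected | 7.1.2 | yes | yes | yes |
| Reported to the sponsor | 7.4 | yes | yes | yes |
| Assessed for seriousness | 7.1.2 (all reported AEs) | yes | yes | yes |
| Detailed recording, including severity and relationship | 7.1.3 | yes | yes | not named |
| Severity rating | 7.2 | yes | yes | not named |
| Relationship rating | 7.3 | yes | yes | not named |
| Summary by severity and relationship | 10.3.4 | yes | yes | yes |

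1. Discontinuation AEs divide into (a) those that are also SAEs or AESIs and (b) those that are neither.
2. Group (a) is rated under 7.2 and 7.3. It is not small by construction. Table 2 includes non-serious opportunistic infections, all malignancies, worsening of psoriasis, and hepatic and hematologic events that end therapy.
3. Group (b) reaches the database through 7.1.2 and 7.4. The only assessment that the protocol requires for every reported AE is seriousness (7.1.2). Where the protocol intends a duty to cover all AEs it says so, and it does not do so for severity or relationship.
4. Section 10.3.4 includes group (b) in its summary, so the gap is exactly group (b).
5. The narrower collection in the direct to HCP process does not change this, because the 10.3.4 analysis excludes that process.

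The protocol gives no number or expected rate for group (b), so its size cannot be calculated.

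**The case against.** The strongest reply is that the gap is one of wording. The case report form and completion workbook are not shown. The Adverse Event form carries both ratings for SAEs and AESIs, and may be used for discontinuation events too. Nothing forbids rating them. The affected output is also only part of one descriptive summary. The event tabulations and rates in 10.3.1 to 10.3.3, the standardized incidence ratios and the lymphoma sample size need neither rating.

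Much of this stands, and it limits the point. It does not remove it: if the form does ask for the ratings, then 7.1.3, 7.2 and 7.3 describe the collection wrongly and still need correcting.

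A reader might infer two stronger things. The first is that the third class has no data behind it. The documents contradict this, because the events are collected and reported and group (a) is fully rated.

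The second is that, because Table 1 names only SAEs and AESIs, discontinuation events will be under-counted. The documents do not support that either. Section 7.4 requires the reason for any permanent discontinuation to be recorded, Section 6.5 and Table 1 have psoriasis medication recorded at the scheduled visits, and 7.1.2 and 7.4 separately require collection and reporting. A row label does not override those duties, and Table 1 says nothing about which ratings are made.

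**Conclusion.** The inconsistency is real and narrow. For discontinuation AEs that are neither serious nor AESIs, the protocol requires no severity or relationship rating, while Section 10.3.4 promises a summary by both. That part of the summary would be missing or filled inconsistently across sites.

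The conclusion about the protocol text rests only on its wording. The consequence for the data also assumes that sites follow Sections 7.1.3 to 7.3 as written and that the unseen forms do not ask for more. Event counts and rates are not shown to be affected. The correction is worth making because it is specific and cheap, and because the ratings are best made when the event occurs.

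**What to change.** Preferred: add AEs that lead to permanent discontinuation to the rating sentences of 7.2 and 7.3, and to the severity and relationship items recorded under 7.1.3. Align the monitoring sentence in Section 7.0 and the label of the Table 1 safety row with 7.1.2 and 7.4.

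The edit should be confined to the ratings. Replacing the class wording throughout 7.1.3 and 7.3 would bring in the full list of detailed recording items. It would also extend the 7.3 duty to follow possibly or probably related events until they resolve or stabilize, which should be left unchanged.

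The cost is two extra ratings per such event, the protocol wording, and the form and its completion guide where they do not already ask for them. No visit is added.

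Alternative: limit the last sentence of 10.3.4 to SAEs and AESIs. This adds no work at sites, but gives up the severity and relationship summary for the other events that ended therapy.

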10.3.5 Subgroup Analysis of Adverse Events

A summary of SAEs, AEs of Special Interest and AEs that lead to permanent discontinuation of HUMIRA® will be provided by the following:

- 1. By geographic locations.
- 2. By types of physician practices.

For patients exposed to concomitant medications of interest. The categories of
concomitant medications of interest that will be captured include phototherapy,
systemic biologics, systemic non-biologics and PUVA.

[figure not shown]
In addition, the analysis of Observational AEs and the analyses of All Treatment-emergent AE will be performed for the New Prescription Patient Population.

10.4 Effectiveness Analyses

Effectiveness parameters measured in this registry for patients enrolled in the US include: Physician's Global Assessment (PGA), Dermatology Life Quality Index (DLQI), Patient Health Questionnaire PHQ-9 For Depression (PHQ-9), Healthcare Resource Utilization, Work Productivity and Activity Impairment (WPAI:SHP), Rosenberg Self-Esteem Scale, Census Socio-Demographic Questionnaire, Medical Outcomes (MOS)-Social Activities Scale, Psoriasis Impact and Experience, Illness Cognition Questionnaire, Insurance Status, and Patient Global Assessment.

[figure not shown]
Descriptive statistics will be provided for the following variables according to the collection schedule outlined in Table 1:

- 1. PGA:
 - a. Proportion of patients achieving "clear."
 - b. Proportion of patients achieving "clear or minimal."
- 2. DLQI:
 - a. Proportion of patients achieving DLQI = 0.
 - b. Proportion of patients achieving DLQI = 0 or 1.
 - c. Change from baseline in DLQI.
- 3. PHQ9:
 - a. Change from baseline in PHQ9 total score.
- 4. Health Resource Utilization

- a. Proportion of subjects who had at least one event (e.g., hospitalization, ER, physician visits).
- b. Average number of events occurred per subjective who had at least one event.
- 5. WPAI-SHP: Change from baseline in the four impairment percentages:
 - a. Percent work time missed.
 - b. Percent impairment while working.
 - c. Percent impaired activity.
 - d. Percent overall work impairment.
- 6. Rosenberg Self-Esteem Scale: change from baseline in total score.
- 7. Census Socio-Demographic Variables: proportion of subjects in each category.
- 8. Medical Outcomes (MOS)-Social Activities Scale: change from baseline.
- 9. Psoriasis Impact and Experience: proportion of subjects who strongly agree, agree, not sure but probably agree, not sure but probably disagree or strongly disagree with any of the statements.
- 10. Illness Cognition Questionnaire: change from baseline in helplessness sub-score, acceptance sub-score and total score.
- 11. Insurance Status: proportion of subjects uninsured, or insured in any of the plan types.
- 12. Patient Global Assessment:
 - a. Proportion of patients achieving "Complete disease control."
 - b. Proportion of patients achieving "Complete disease control or good disease control."

Effectiveness data will be analyzed as observed, as this is an observational registry. Number of patients with non-missing baseline and visit values, baseline mean, visit mean,

mean and standard deviation of change from baseline will be provided for continuous variables. Counts and percentages will be provided for categorical variables.

The effectiveness data will be summarized for the All Treated Patient Population (from the first dose in the registry) and the New Prescription Patient Population. For patients with TI, effectiveness summaries will combine data from all Treatment Periods, excluding the measurements from 14 days after the last dose during a treatment period up to the first dose in the subsequent Treatment Period.

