6.5 Registry Conduct

Physicians will be provided with a registry kit that includes a protocol, patient informed consent forms, access to electronic Case Report Forms (eCRFs), including SAE Report Forms, specially designed eCRFs to collect AEs of Special Interest and paper patient

questionnaires to collect Patient Reported Outcomes (PRO) (United States only). Physicians will determine the appropriate therapy for each patient in accordance with the locally approved label. The decision to prescribe HUMIRA® to the patients should be made separately from, and prior to the decision to enroll them into the registry.

The physician will follow the patient during regular office visits at intervals as determined by routine clinical practice or as recommended by national guidelines.

At the enrollment (baseline) visit, the physician will complete the Enrollment eCRFs by obtaining and recording all of the available required information. All SAEs and AEs of Special Interest (Table 2) that occurred since the first commercial dose of HUMIRA® will be collected on a specially designed questionnaire/source document for entry into EDC.

Information about medications taken for Psoriasis will be recorded on the eCRF at enrollment and during the regularly scheduled visits that are closest to Months 3, 6, 12, 18, 24, and every 6 months thereafter through Month 120. While the physician may deem it appropriate and necessary to have the patient return for additional visits during the observation period, data will be collected via electronic Case Report Forms (eCRFs) only at the intervals that most closely correspond to those described above. However, information related to safety should be captured at any time using the appropriate eCRFs.

Physicians should treat their patients as they would in their routine clinical practice. At any time, patients and physicians may choose to interrupt HUMIRA® therapy for any reason. Patients that intermittently stop treatment (Section 10.1) should continue to be monitored during their treatment interruption for safety (SAEs and AEs of Special Interest) and effectiveness, if applicable. These patients will be questioned for changes in their psoriasis medications and medical history at their regularly scheduled visits.

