Appendix E. Patient Health Questionnaire PHQ-9 For Depression

PATIENT HEALTH QUESTIO	NNAIRE	- 9			72883
THIS SECTION FOR USE B	SY STUDY PE	ERSONNE	L ONLY.		
Were data collected? No ☐ (provide reason in comment	's)				
If Yes , data collected on visit date \square or specify da	te:	Mon-YYYY			
Comments:	55-1	mon-1111			
Only the nations (authors) should an	tou informa	tion onto	this augs	tionnoiro	
Only the patient (subject) should en	ter iniorina	lion onto	triis ques		•
Over the last 2 weeks , how often have you been by any of the following problems?	bothered	Not at	Several days	More than half the days	Nearly every day
Little interest or pleasure in doing things		0	1	2	3
2. Feeling down, depressed, or hopeless		0	1	2	3
3. Trouble falling or staying asleep, or sleeping too	much	0	1	2	3
4. Feeling tired or having little energy		0	1	2	3
5. Poor appetite or overeating		0	1	2	3
Feeling bad about yourself — or that you are a fa have let yourself or your family down	0	1	2	3	
7. Trouble concentrating on things, such as reading newspaper or watching television	0	1	2	3	
Moving or speaking so slowly that other people c noticed? Or the opposite — being so fidgety or r you have been moving around a lot more than us	0	1	2	3	
Thoughts that you would be better off dead or of yourself in some way	hurting	0	1	2	3
		Scoring Fo	OR USE BY S	TUDY P ERSOI	INEL ONLY
		+	+	+	·
			=	Total Score	»:
If you checked off any problems, how difficult have these problems made it for you to do your work, take care of things at home, or get along with other people?					
Not difficult Somewhat at all difficult □		Very fficult □		Extreme difficu	• 1
Developed by Drs. Robert L. Spitzer, Janet B.W. Williams, Kurt Copyright © 2005 Pfizer, Inc. All rights reserved. Reproduced w		lleagues, with	an education	nal grant from EP10905.PHQ9P	Pfizer Inc.
I confirm this information is accurate. Patient's/	Subject's initi	ials:	Date:		

Appendix F. Health Care Resource Utilization (Unscheduled Outpatient Visits, Emergency Room Visits and Hospitalizations)

1. Since the last study visit has the subject had any physician/health care visits for their Chronic Plaque Psoriasis other than the protocol visits?
☐ No ☐ Yes (if yes provide the following)
If yes provide the following:
I. Since the last visit, has the subject been seen by a physician for his/her Psoriasis?
YES: NO: If YES, how many times:

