II. Since the last visit, has the subject been seen in the Emergency Room for his/her Psoriasis?
YES: NO: If YES, how many times:
III. Since the last visit, has the subject been admitted to the hospital due to his/her Psoriasis?
YES: NO: If YES, how many times: IF YES, please indicate the total number of days in the hospital:

Work Productivity and Activity Impairment Questionnaire: Specific Health Problem V2.0 (WPAI:SHP) Appendix G.

TDI C	11 '	,•				.1	CC .	c	_	NG OT	 .	u c	1.99.
								•					your ability to work
and pe	_												mber, as indicated.
1.	Are you cu If NO,									? _		NO _	YES
The no	ext question	ns are	abo	ut th	e pa	ast so	even	days	, not	incl	ludin	g toda	y.
2.	problems a	associ s you	ated wen	l witl t in l	n yo ate,	ur Pa left	SOR] early	[ASI] , etc.	S ? I , bec	nclu ause	de ho	ours yo	m work because of ou missed on sick SORIASIS. Do not
	НО	URS											
3.	_	-			•					•			m work because of ipate in this study?
	HO	URS											
4.	During the	e past	seve	en da	ys,	how	man	y hou	ırs di	id yo	ou ac	tually	work?
	HO	URS (If "()," sl	kip t	o qu	estio	n 6.)					
5.	During the productivi								you	r PS	ORL	ASIS a	affect your
	Think about days you were limited in the amount or kind of work you could do, days you accomplished less than you would like, or days you could not do your work as carefully as usual. If PSORIASIS affected your work only a little, choose a low number. Choose a high number if PSORIASIS affected your work a great deal.												
			Co				w mu						
				pro	duct	ivity	while	you	were	wor	king .		
	IASIS had ect on my	0	1	2	3	4	5	6	7	8	9	10	PSORIASIS completely prevented
WOIK						CIRC	TE 4	NII	MRF	(R			me from working
	CIRCLE A NUMBER												

6. During the past seven days, how much did your PSORIASIS affect your ability to do your regular daily activities, other than work at a job?

[figure not shown]
By regular activities, we mean the usual activities you do, such as work around the house, shopping, childcare, exercising, studying, etc. Think about times you were limited in the amount or kind of activities you could do and times you accomplished less than you would like. If PSORIASIS affected your activities only a little, choose a low number. Choose a high number if PSORIASIS affected your activities a great deal.

Consider only how much PSORIASIS affected your ability to do your regular daily activities, other than work at a job.

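### Resource use is summarised by visit with no allowance for recall length, so a change in the recall window (Month 6 to Month 12 on the literal reading) can look like a rise in use

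*Protocol*

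**What the plan says.** Section 10.4, item 4, lists two summaries of healthcare resource utilization. Item 4a is the "Proportion of subjects who had at least one event (e.g., hospitalization, ER, physician visits"). Item 4b is the "Average number of events occurred per subjective who had at least one event". Both are tied to the visit schedule: "Descriptive statistics will be provided for the following variables according to the collection schedule outlined in Table 1". Effectiveness data are analysed as observed, and no time denominator is given for this item.

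The form in Appendix F has no fixed recall period. Its lead question reads "Since the last study visit has the subject had any physician/health care visits for their Chronic Plaque Psoriasis other than the protocol visits"; the follow-up questions use a shorter anchor, for example "Since the last visit, has the subject been seen in the Emergency Room for his/her Psoriasis".

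Section 6.5 places data collection at the "regularly scheduled visits that are closest to Months 3, 6, 12, 18, 24, and every 6 months thereafter through Month 120". In Table 1 the resource-use form is completed at enrollment, is left blank in the first month column, is marked in the next two, and is completed again at completion or premature discontinuation. By the visit list these month columns are Months 3, 6 and 12. From there note c applies: "Data collected at annual visits only (i.e., Months 24, 36, 48, 60, 72, 84, 96, and 108"). Note a adds that timing is approximate: "Data collection at regular visits that are closest to time points described".

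**The concern.** A count of events since the last visit depends on how long ago that visit was. If the interval changes between collection points, the percent with any event and the mean count among users both change even when patients use care at a steady rate. The two planned summaries would then show a step that belongs to the form and the schedule, not to the patients, and a real decline across that step could be read as an increase.

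The windows are uneven in three ways:

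- The scheduled gap before the form is not the same at all collection points.
- A form completed at premature discontinuation covers whatever time has passed since the previous visit, and it shares a Table 1 column with Month 120.
- The enrollment form has no earlier registry visit to count from.

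Visit timing also varies between patients. At stake is the early part of a descriptive series that serves the secondary objective of long-term effectiveness in US patients.

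**Working it through.** The protocol states no rate of resource use and no figure for this item, so there is nothing to reproduce. The rates below are assumptions.

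**Recall windows**

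- Visits (Section 6.5): Months 3, 6, 12, 18, 24, then every 6 months.
- Resource-use forms (Table 1 and note c): enrollment, Months 6 and 12, then yearly, and at completion or premature discontinuation.
- Reading A, anchor is the previous registry visit. Month 6: 6 − 3 = 3 months. Month 12: 12 − 6 = 6 months. Month 24: 24 − 18 = 6 months, and likewise for later scheduled forms.
- Reading B, anchor is the previous resource-use form. Month 6: 6 months. Month 12: 6 months. Month 24: 12 months.

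On either reading one step doubles the window.

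**Formulas.** For a constant rate r per year and a window of w years, m = r × w events are expected.

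- Percent with any event (4a): 1 − exp(−m)
- Mean among users (4b): m / (1 − exp(−m))
- Mean over all patients: m

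**Constant use, Reading A (w = 0.25, then 0.5)**

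| Rate per year | 4a, Month 6 | 4a, Month 12 | Ratio | 4b, Month 6 | 4b, Month 12 | Ratio |
|---|---|---|---|---|---|---|
| 0.2 | 4.9% | 9.5% | 1.95 | 1.025 | 1.051 | 1.025 |
| 0.5 | 11.8% | 22.1% | 1.88 | 1.06 | 1.13 | 1.06 |
| 1.0 | 22.1% | 39.3% | 1.78 | 1.13 | 1.27 | 1.12 |

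Over a wider range of 0.1 to 4 events per year, the 4a ratio runs from 1.98 down to 1.37 and the 4b ratio from 1.01 up to 1.46. With overdispersed counts (negative binomial, k = 0.5, so 4a = 1 − (1 + m/k)^(−k)), the ranges are 1.93 to 1.31 and 1.04 to 1.53.

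**Constant use, Reading B (w = 0.5, then 1.0).** At 0.2 per year, 4a goes from 9.5% to 18.1% (1.90 times) and 4b from 1.05 to 1.10. At 1.0 per year, 4a goes from 39.3% to 63.2% (1.61 times) and 4b from 1.27 to 1.58. The distortion in 4a is somewhat smaller and comes later.

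**A true fall.** Let the rate fall by a fraction f across a step that doubles the window. The expected count goes from r × w to r × (1 − f) × 2w. This is an increase whenever 2(1 − f) > 1, that is f < 0.5. Both 4a and 4b increase with m, so any fall of less than 50% shows as a rise in both. Example on Reading A at 1.0 per year with f = 0.3: m goes from 0.25 to 1.0 × 0.7 × 0.5 = 0.35, so 4a goes from 22.1% to 29.5% and 4b from 1.13 to 1.19.

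**With a time denominator.** Events divided by recall time is m / w = r. Constant use gives a ratio of 1.00 across the step, and the 30% fall shows as 0.70.

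**The users-only mean at equal recall.** Suppose 20% of patients have 1 event and 20% have 3. Then 4a = 40%, 4b = (0.2 × 1 + 0.2 × 3) / 0.4 = 2.0, and the mean per patient is 0.8. If the 1-event users drop to none, 4a = 20%, 4b = 3.0, and the mean per patient is 0.6. The product 4a × 4b recovers the fall: 0.4 × 2.0 = 0.8 and 0.2 × 3.0 = 0.6.

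**The case against.** Several points on the other side are sound.

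- **The step depends on a reading.** The lead question refers to the last study visit and the follow-up questions only to the last visit. If patients count from the previous form, Months 6 and 12 match. This stands, but the step then moves to Month 24 and does not vanish.
- **A reader might infer that constant use would appear to double.** It would not. Neither planned summary doubles. Only the mean over all patients does so exactly, and that is not a listed summary. The percent with any event approaches two-fold only when use is infrequent.
- **A reader might infer that the series cannot show long-term change.** On the literal reading Months 12 to 120 share a nominal 6-month window, so only Month 6 is out of line among the scheduled follow-up forms. Drift in visit timing and discontinuation forms add irregularity, but the later series remains broadly comparable.
- **A reader might infer that the users-only mean should be dropped.** Items 4a and 4b together form an ordinary two-part summary, and within an event category their product gives the mean per patient. Nothing in the protocol shows that light users stop first, and under the Poisson model at equal recall the users-only mean falls when use falls. The product is still not adjusted for time, so it does not remove the main problem.
- **No baseline comparison is listed for item 4.** Change from baseline is named for other items, not this one. The caution about the enrollment form is therefore preventive.
- **A rate could be added in the SAP.** It could. But the protocol states these two summaries for these collection points, and as stated they mislead across one step.

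**Conclusion.** The point holds as a minor one. The two summaries in item 4, combined with a since-last-visit form and an uneven schedule, produce an artificial rise at one step: Month 6 to Month 12 on the literal reading, Month 12 to Month 24 if the anchor is the previous form. For constant use of 0.2 to 1.0 events per year, the percent with any event rises 1.78 to 1.95 times on the literal reading and 1.61 to 1.90 times on the other, with a smaller rise in the mean among users. A true fall of less than 50% across the step is shown as an increase.

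The sizes rest on an assumed rate, a Poisson count and nominal visit times. The direction, and the 50% threshold for a window that doubles, do not depend on the assumed rate. The item is descriptive, US-only and secondary, with no test attached. The primary safety analysis is unaffected.

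**What to change.** In Section 10.4, item 4, or in the SAP:

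1. Keep 4a and 4b.
2. Add, for each category (physician, emergency room, hospital), events per 100 patient-years of recall time by collection point. The numerator is all events on completed forms. The denominator is the summed time from the previous registry visit date to the form date, with zero-event patients included. This matches the events-per-100-patient-years convention already used for adverse events in Section 10.3.
3. State explicitly which visit anchors the recall.
4. Do not compare the enrollment form with later visits, since its window is undefined.

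The cost is one extra summary. The form already asks for counts, and case report forms are completed at every scheduled visit, so the dates should be available without new data collection. The rate relies on the previous registry visit being the true anchor. Section 6.5 allows extra office visits on which scheduled data are not collected, and a patient who counts from one of those would have a shorter window than the denominator assumes.
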